5 STUDY INTERVENTIONS

5.1 Interventions, Administration, and Duration

CAPABLE Transitions overview: *CAPABLE Transitions* is informed by theory and evidence-based practices (Table 1) and consists of ≤ 11 in-home visits by an OT and RN over three months. Every participant that completes the *CAPABLE Transitions* intervention will receive each component of the intervention (e.g., care transitions assistance, assessment, education, problem-solving activities), but the interventionists will tailor the content to each participant's goals and risk profile. University of Rochester Medicine Home Care will document information about study participation in the older adults' electronic health records. Table 2 provides a detailed overview of the intervention timeline and content. The RN/OT visits will occur as soon as possible following the minimum possible number of weeks after the prior visit. The study visit timeline will be flexible to accommodate for both the interventionists and the participants needs. In instances where there is a deviation from our protocol, we will complete a Note to File in our regulatory file (e.g., if an interventionist is on sick leave or if the participant has been hospitalized). To help ensure fidelity to the intervention, the Study OT and RN will

complete standardized training for *CAPABLE* provided by Johns Hopkins School of Nursing. We will augment this training with training specific to *CAPABLE Transitions* that accounts for the care transitions RN visit and other adaptations we are making to *CAPABLE* (e.g., increased frequency of visits early on, involvement of a Study Partner).

Table 2. CAPABLE Transitions timeline and content.

| Session | Timing | Content | Interventionist (OT, RN, Handyworker) Follow-up |
|-----------------------------|---|---|--|
| Occupational Therapy | | | |
| Visit #1 | As soon as possible after RN visit #1 (or, in some unusual circumstances, as soon as possible after CHHA admission) | Introduction to OT portion of CAPABLE. Issue intervention folder. Function-focused OT assessment, including functional mobility, ADL, and IADL. Determine participant's functional goals. Physical therapy screen. | |
| Visit #2 | As soon possible after visit #1 ideally 1-2 wks after OT #1 | Fall risk and recovery education. Conduct home safety assessment and identify necessary repairs or modifications. | Develop work order for home repairs/modifications for handyworker. |
| Visit #3 | As soon possible after visit #2, ideally 1-2 wks after OT #2 | Brainstorm and develop action plan with participant for participant-identified goal #1 (e.g., safely bathing, going upstairs, and preparing food). | |
| Visit #4 | As soon possible after visit #3, ideally 1-2 wks after OT #3 | Review action plan #1. Brainstorm and develop action plan with participant for participant-identified goal #2. Review handyworker work and train participant on new assistive devices as able. | Issue assistive devices or medical equipment as available. |
| Visit #5 | As soon possible after visit #4, ideally 2-4 wks after OT #4 | Review action plan #2. Brainstorm and develop action plan with participant for participant-identified goal 3. Issue assistive equipment and durable medical equipment (if not already done) and train participant on new assistive devices and modifications. | |
| Visit #6 | As soon possible after visit #5, ideally 3-4 wks after OT #5 | Review OT section of the Flipbook. Help participant generalize solutions for future problems and problem-solving techniques. Review goals and participant's achievement of them. Review readiness score. Ask if participant has any final questions. | |
| Handyworker | | | |
| Visit #1 | As soon as possible after OT #3 | Visit home to assess which materials to purchase for ordered modification and repairs. For common types of repairs and modifications involving materials on hand, begin repairing and modifying the home. | |

| | | | |
|-------------------------|---|--|---|
| Visit #2 | Once supplies are available | Repair and modify home based on participant goal-prioritized work order. | Notify OT when this is complete. |
| Registered Nurse | | | |
| Visit #1 | As soon as possible after client has been admitted to Certified Home Health Agency (CHHA) | 
CHHA clients and RN work together to:
 
 1) Create list of medical providers, recent or scheduled appointments, and barriers to attending appointments; RN assists clients in overcoming barriers and linking to outpatient medical services. 2) Identify key symptoms as well as questions and concerns for their medical providers; RN assists clients in communicating with medical providers. 3) Complete a comprehensive medication management assessment. Based on the assessment, RN assists the client in developing strategies to more effectively manage medications. 4) Complete a health-related social needs questionnaire²³; based on the screener, RN completes referrals for identified health-related social needs. | 
If indicated:
 
 1) Correspond with outpatient medical providers to communicate concerns or schedule an appointment. 2) Assist with referral to community-based agencies or CHHA social worker. 3) Connect with medical transportation services. 4) Communicate medication concerns to study pharmacist and/or outpatient providers. |
| Visit #2 | As soon possible after visit #1, ideally 1-2wks after RN #1 | 
Introduction to RN portion of CAPABLE. Function-focused RN assessment including pain, mood, strength, balance, medication information, and need for health care provider (e.g., PCP) advocacy/communication.
 | Correspondence to PCP if necessary. |
| Visit #3 | As soon possible after visit #2, ideally 2--4 wks after RN #2 | 
Determine goals in RN domain together. Start to brainstorm goal #1 (e.g., pain in standing, fall prevention). Demonstrate CAPABLE exercises. Review medication calendar. Discuss participant/PCP communication.
 | Correspondence to PCP if necessary. |
| Visit #4 | As soon possible after visit #3, ideally 22-4 wks after RN #3 | 
Complete brainstorming/problem-solving process. Develop action plans for identified goals with participant. Assess PCP response to communication of participant needs. Review, assess, and troubleshoot exercise regimen. Issue health care passport.
 | Correspondence to PCP if necessary. |
| Visit #5 | As soon possible after visit #4, ideally 2-4 wks after RN #4 | 
Review progress and use of strategies for all target areas. Issue and review RN section of Flipbook that summarizes program. Evaluate achievement of goals and readiness to change scale. Help participant generalize brainstorming process for future health issues. Discuss participant/PCP communication. Ask if participant has any final questions.
 | Correspondence to PCP if necessary. |

Intervention delivery characteristics: *CAPABLE Transitions* consists of an OT-led multidisciplinary team in which the study OT (≤ 6 visits), RN (≤ 5 visits), and handyworker (≤ 2 visits) deliver an in-home intervention over approximately three months with each OT and RN visit lasting about 60-90 minutes. The OT and RN visits are more frequent earlier in the intervention to assist older adults with the hospital or post-acute care facility-to-home transition. We gradually increase the timing interval between visits so that participants have time to practice strategies or activities following the in-home sessions. All study participants who decide to receive the full dose of the intervention will receive a total of 6 OT visits and 5 RN visits. The number of handyworker visits will depend on the modifications and repairs that are needed by the participant (e.g., if everything can be completed in 1 visit, then participants only will have 1 handyworker visit). There may be rare instances for which the handyworker visits the home more than twice (e.g., perhaps the participant has a change in functioning during the course of the intervention that would benefit from an additional home modification). Additionally, the handyworker services may be unnecessary for all participants (e.g., some participants may decline handyworker services if they already live in an age-friendly home or community). While receiving the study intervention, CHHA clients also will receive CAU from the CHHA (which may include OT services). The study OT and RN will be the same clinicians who deliver CHHA CAU. To do so, they will either lengthen the CAU visit or have a separate visit solely for the intervention. Data from the CHHA indicate that the median length of a home health episode of care is 29 days (Q1: 17 days, Q3: 47 days). For study participants who complete the *CAPABLE Transitions* intervention, we anticipate that most will complete the OT and RN sessions in approximately 90 days, and the intervention sessions will not continue past 5 months following hospital or post-acute care facility discharge (unless there is an exception noted in a Note to File document). Therefore, we expect that the majority of study participants will have CHHA CAU that temporarily overlaps with the *CAPABLE Transitions* intervention. We anticipate that there will be minimal “leakage” of the study intervention services to the CHHA CAU because the OT and RN actions for *CAPABLE Transitions* will follow a manual based on *CAPABLE* training and these actions are markedly different from their usual CHHA CAU roles.

The clinical research coordinator (CRC) will maintain a calendar to facilitate coordination of the intervention and ensure that study visits occur as detailed in the study protocol. A secure share site (UR Box) that can be remotely accessed will enhance communication between the OT, RN, and handyworker. This site also will enable study staff to monitor electronic documentation for study fidelity and to help assess study costs. The OT will have responsibility for case coordination with the CHHA staff and other interventionists and for identifying the necessary supplies to order, which include home modifications and repairs. Monthly to bimonthly meetings with the OT, RN, handyworker, CRC, and PI will ensure communication, adequate supervision, and appropriate fidelity to the intervention.

Of note, CHHA clients and dyads will determine the dose of the intervention (e.g., number of visits) and whether to participate in the various components of the intervention (e.g., types of visits such as OT, RN, and handyworker services). More specifically, after each OT or RN visit, the study participants will be asked whether they would like to continue with the intervention. The study participants can thereby determine the dose of the intervention they receive as they can discontinue participation in the intervention at any time (see Section 8 for additional detail regarding intervention discontinuation), but still continue their participation in the study assessments. Our interventionists may also terminate the study intervention if identified goals are completed (or unable to be completed) and there are no further participant-interventionist agreed-upon goals to work on.

As previously stated, the study interventionists are practicing home health clinicians that are highly experienced working with older adults who have cognitive impairment. Our study's goal is to improve home safety and functioning and the intervention is catered directly to the needs, ability, and goals of the participants – no two participants will receive the same intervention. The clinicians will not have participants perform exercises or tasks that are unsafe or beyond their ability.

The different intervention components include:

- RN care transitions home visit
- OT comprehensive assessment and development of client-prioritized functional goals
- client-OT work towards addressing functional goals
- handyworker home safety repairs
- handyworker home modifications to support patient-prioritized functional goals
- RN in-depth assessment on pain, depression, strength/balance, medication concerns, and outpatient medical provider communication and development of client-prioritized goals as they relate to these issues
- client-RN work on addressing RN domain goals

Intervention protocol, OT: This OT intervention protocol was adapted from the original CAPABLE intervention.⁴⁰ The OT meets with participants for up to six sessions within approximately three months of randomization.

In the 1st and 2nd OT sessions, the OT meets with participants and conducts a semi-structured clinical interview using the Client-Clinician Assessment Protocol (C-CAP) that has been tested for its psychometric properties for use in home-based and home modification programs.⁵⁷ The C-CAP provides a systematic approach from which to identify and prioritize performance areas that are problematic to participants. For each performance area identified, the OT observes the participant's performance and evaluates safety, efficiency, difficulty, and presence of environmental barriers and supports. The OT will provide a three-ring binder (CAPABLE notebook) which will contain educational materials, contact information and a calendar to integrate the sessions by the RN and handyworker interventionists. Also, in the course of this session, the OT assesses the environmental home safety (common safety and mobility risks include holes in walkways, uneven carpeting, and absent railings or banisters). Based on the environmental assessment, observation of ADL activities, and identification of the participant's goals, the OT and participant discuss possible environmental modifications. The OT then creates a list of agreed upon assistive devices and housing repairs for the handyworker.

In 3rd, 4th, and 5th OT sessions, the OT engages the participant in problem-solving to identify behavioral and environmental contributors to performance difficulties and strategies for attaining functional goals. The OT trains participants to use specific strategies such as energy conservation techniques, simplifying tasks and the environment, and using assistive devices. Also, the OT provides balance and fall recovery techniques to decrease fear of falling. In each session, the OT reinforces strategy use, reviews problem-solving, refines strategies, and provides education and resources to address future needs. Home modifications (grab bars, rails, raised toilet seats) are coordinated with the handyworker to assure that they are provided in a timely manner and meet the needs of the participant. The OT follows up with training in their use.

In the final (6th) OT session, the OT reviews all techniques, strategies and devices, and helps the participant to generalize success to other situations.

Intervention protocol, RN: This RN intervention protocol was adapted from the original CAPABLE intervention.⁴⁰ The RN meets with participants for up to five sessions within approximately three months of randomization.

In the 1st RN session, the RN meets with the participants and works with the CHHA client to create a list of medical providers and scheduled appointments and to identify any barriers to attending outpatient medical appointments. The RN emphasizes the importance of follow-up outpatient appointments and works with the participant to address barriers to attending appointments or any questions the participants may have for the medical providers. At this initial visit, the RN also assesses the participant's medications as well as the participant's ability to manage her own medications and tailors intervention as indicated by the assessment. Additionally, the RN will work with the participant to identify key symptoms and signs to monitor for that should prompt an urgent medical work-up. Lastly, the RN conducts a health-related social needs screener and works with the participant to make appropriate referrals to community resources as needed.

The 2nd RN session occurs approximately 2-3 weeks after the first RN session. In this session, the RN assesses the participant using the C-CAP RN developed specifically for CAPABLE in which the RN focuses on how and whether pain, depression, strength and balance, medication management, and communication with PCP impact daily function.⁵⁸ In this assessment, the RN and the participant identify and prioritize goals, and make plans to achieve those goals. The RN also adds educational resources to the CAPABLE notebook to reinforce its use as a resource.

In the 3rd and 4th RN sessions, the RN and the participant work on the goals identified through the C-CAP RN. In each session, the RN reinforces strategy use, reviews problem-solving, refines strategies, and provides education and resources to address future needs (e.g., pill box for medication management).

In the final (5th) RN session, the RN reviews the participant's strategies and helps to generalize them to other possible challenges.

Intervention protocol, handyworker: This handyworker intervention protocol was adapted from the original CAPABLE intervention.⁴⁰

The hand worker portion is contracted through handyworker services provided by a local non-profit aging services agency, Lifespan (Lifespan, Rochester, NY). Lifespan has a program entitled, "Home-Safe-Home," which has been available to the community for over 20 years.⁵⁹ The Home-Safe-Home Program provides home modifications such as grab bars, tub grips, shower seats, handheld showers, commodes, railing modifications, and other simple yet effective modifications that reduce the risk of falling. It modifies approximately 900-1000 homes a year. This program is funded in part through grants from various organizations. In an evaluation of this program, 82 (94%) of surveyed Home-Safe-Home participants reported feeling more comfortable in their home since the home modifications and 57 (65.5%) reported increased independence, most frequently with bathing (68.4%), followed by use of the bathroom and stairs (49.1%).⁶⁰ To deliver the Home-Safe-Home Program, Lifespan employs a handyworker (the current handyworker has been in this role since 2014). Upon agreeing to participate in this study and after being randomly assigned to the CAPABLE *Transitions* intervention arm, study participants will be enrolled in Lifespan's Home-Safe-Home Program. Lifespan also has liability insurance for this program and, should any participants have problems with the handyworker

modifications or installations, they can follow-up with Lifespan and the handyworker. Of note, study participants will not need to identify themselves to Lifespan as they will be enrolled in the Home-Safe-Home Program via their participation in our study. Furthermore, the handyworker, [name], is Lifespan's Home-Safe-Home Program coordinator and will be doing the handyworker modifications for all of our study participants. As such, additional study communication with Lifespan will not be needed as Lifespan will be fully aware of all of the study participants' involvement in the Home-Safe-Home Program as well as their participation in our study. We will pay Lifespan to deliver the Home-Safe-Home handyworker services to our CAPABLE Transitions participants. The handyworker will help coordinate the ordering of the assistive devices as well as the repair and modification supplies. The handyworker has extensive experience working with older adults in the area, and will make as many home visits as it takes to provide the study renovations/modifications. The budget for home repairs, home modifications, and assistive devices is \$1,200 per household, similar to CAPABLE's \$1,300,⁴⁰ an amount that was adequate for most renovations necessary for safer, more functional homes. We also have extra funds available if necessary, for unusual situations (e.g., if we need to replace or repair equipment we purchased/installed during the course of the study).

If home repairs or modifications outside the Handyworker's scope of practice are indicated (e.g., plumbing, carpentry, or electrical work), participant compensation may include additional cash payments for home repair and modification services performed through Catholic Family Center's HomeWorks Program. HomeWorks is a program that provides low-cost home maintenance/repair support to older adults. These additional cash payments of \$100 would cover the expense of enrolling in HomeWorks (for 3 months) and obtaining an initial estimate of the cost of the modifications/repairs and/or the expense of minor home repairs and modifications that are recommended and agreed upon by our study interventionists and performed by Catholic Family Center's HomeWorks contractors. Of note, HomeWorks limits the maximum service charge to \$500. As many of the participants may not have funds available to pay for the costs of these services upfront, the study team will provide this compensation to the participants in cash prior to having the participants pay for these services (maximum compensation for HomeWorks services would be \$500 per participant, and is included in the \$1,200 budget for home repairs/modifications and assistive devices). Participants will be notified at time of informed consent that depending on the amount they are paid, they may be asked to submit a W-9 form, which includes their Social Security Number. No repairs or modifications to the participants' homes, however, will be made without the participants' permission.

Similar to above, if larger home repairs or modifications outside of both Lifespan and Catholic Family Center's scope of practice are indicated (e.g., masonry, bathroom remodeling), participant compensation may include additional cash payments for home repair and modification services performed by another person (e.g., a handy worker or separate contractor) or agency (e.g., bathroom remodelers) within our allowed budget. This will allow participants to complete indicated home repairs or modifications that are outside the scope of both Lifespan and CFC capabilities. We will only reimburse participants for agreed upon repairs and modifications that are consistent with the objectives of the CAPABLE Transitions intervention. Additionally, we plan to obtain an estimate of the work prior to agreeing to reimburse it. These additional cash payments would cover obtaining an initial estimate of the cost of the modifications/repairs as well as the expense of the home repairs and modifications that are recommended and agreed upon by our study interventionists and performed by these contractors or agencies. The total cost of these and other services provided to the participant will not exceed the \$1,200 budget for home

repairs/modifications and assistive devices. In unusual circumstances (e.g., much needed home safety repair), we may also be able to reimburse participants for expenses exceeding \$1,200 if necessary to improve home safety or function and our budget allows. No repairs or modifications to the participants' homes, however, will be made without the participants' permission. Participants will be responsible for any costs that are associated with maintaining or replacing these items following the termination of the study.

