Whereas the first element primarily aims to facilitate the transfer of care from the hospital or post-acute care facility to the outpatient and home settings, *CAPABLE Transitions'* second element seeks to optimize the ability of the older adults to function in their homes. To do so, we modified *CAPABLE* in four ways. First, given the acuity of the older adults our intervention targets, the Study OT and RN visits will occur more frequently in the first few weeks following the transition relative to the original *CAPABLE* intervention (e.g., every 1-2 weeks rather than every 2-4 weeks, with flexibility to account for participant preference, participant availability (e.g., may be hospitalized), and varying CHHA clinical demands). Second, following the transition home, all the CHHA clients in our study will be receiving CHHA nursing services and many also will be receiving CHHA OT services. For CHHA clients randomized to our intervention arm, in addition to CHHA RN +/- CHHA OT services, they will receive *CAPABLE Transitions* RN and OT services delivered by the same CHHA RN and CHHA OT. The *CAPABLE Transitions* intervention can be delivered either at the end of a CAU RN and OT in-home session or at a separate in-home visit. Of note, *CAPABLE Transitions'* OT services focus on client-prioritized functional goals while *CAPABLE Transitions'* RN services target client-prioritized conditions and syndromes that may be impairing function (e.g., depression, pain, incontinence) as well as fall prevention and communication with the PCP. In contrast, CHHA CAU OT and RN services are generally directed by a physician's order and tend to focus on a specific medical problem identified by the physician (e.g., wound care, diabetes management, upper extremity mobility). Third, our intervention will include those with moderate or severe cognitive impairment (including dementia), regardless if they have live-in caregivers, who may potentially live alone. Optionally, we may deliver the intervention to a caregiver-participant dyad, regardless of cognition, if there is a caregiver willing to serve as a study partner. An MMSE score of 20 or less indicates that a moderate or severe cognitive impairment is present.^{44, 45, 86} Fourth, CHHA clients and dyads will determine the dose of the intervention and whether to participate in the various components of the intervention. The different intervention components include:

- RN care transitions home visit

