- Access to Vimeo video clips of visit scenarios
- Access to other CAPABLE sites' outcomes and experiences through an online user group

We will monitor the following fidelity components: intervention adherence, intervention exposure/dose, quality of delivery, participant engagement, and differentiation between critical intervention features.⁶²⁻⁶⁴ Adherence consists of the extent to which intervention components were delivered as prescribed in the study manuals. Exposure considers the number of intervention sessions and the time interventionists spent assisting participants. Quality of intervention delivery considers qualitative aspects of the delivery independent of the intervention content such as interventionist enthusiasm and global estimates of intervention effectiveness. Participant engagement is a measure of participant enthusiasm and degree of participation in the intervention. Intervention differentiation will help us identify which elements of the intervention are essential and a check to make sure that the participants in the intervention only received the plan intervention.⁶⁴ To assess these varied fidelity domains, we will use a combination of direct assessment (e.g., observation via audiotapes) and indirect measures (e.g., OT/RN self-report).⁶² Similar to prior work, we also rely upon a combination of Likert and yes/no items to measure fidelity.⁶⁵ More specifically, the CRC will review the audio recorded intervention sessions and will complete the Likert and yes/no items while listening to the recording (no transcripts of the recordings will be generated). As a group, we will review the fidelity scores generated by the CRC review of the audiotapes during our regularly scheduled *CAPABLE Transitions* meetings and will use these findings to identify any potential issues that the Study OT and RN should address to improve the quality of their administration of *CAPABLE Transitions*. Tracking these fidelity metrics longitudinally should provide us with near real-time feedback to allow us to improve the delivery of the intervention as we move forward. We will use an encrypted voice recorder for this purpose. We will label these audio recordings using de-identified numbers only and will store the recordings on secure University of Rochester servers and/or the CRC and PI's computers. Access to these audio recordings will be password protected and audio recordings will be destroyed consistent with federal guidelines and the University of Rochester RSRB Policy 405.

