| Variable | Variable Type | Assessment Schedule | Data Source |
|--|---------------------------|--------------------------|---|
| Primary Outcomes | | | |
| • Participants Screened, Enrolled, and Retained | Continuous, Proportion | Monthly | Study Documentation |
| • Intervention Fidelity: Adherence, Dose, Quality | Continuous, Proportion | Varies | Audio Recording, Study Documentation, Self-Report |
| • Intervention Perceived Benefit (based on Szanton et al., 2019 ⁴⁰) | Likert Items, Open-Ended | 3, 6 Months | Self-Report, Proxy-Report |
| • Data Completeness for Clinical Outcomes | Proportion | 6 Months | Study Documentation |
| Secondary Outcomes (Primary Clinical Outcomes) | | | |
| • Home Time | Continuous | 3, 6 Months | Chart Extraction, Self-Report |
| • Quality of Life (EQ-5D-5L, ICECAP-O ^{66, 67}) | Variety of Variable Types | Baseline, 3 and 6 months | Self-Report |
| • Service Utilization: ED, Hospital, Nursing Home Use | Continuous | Baseline, 3 and 6 months | Chart Extraction, Self-Report |
| Sociodemographics | | | |
| • Contact Information | Address, Phone Number | Baseline, 3 and 6 Months | Self-Report |
| • Age, Date of Birth | Continuous, Date | Baseline | Self-Report |
| • Race, Ethnicity, Sex | Categorical | Baseline | Self-Report |
| • Formal Education, Marital Status, Living Arrangement, Income, Home Ownership and Type | Categorical | Baseline | Self-Report |
| • Caregiver or Receive Caregiving | Categorical | Baseline, 3 and 6 Months | Self-Report |
| • Children and Siblings | Continuous | Baseline | Self-Report |
| • Health Insurance | Categorical | Baseline | Self-Report |
| Health and Functioning | | | |
| • Social Needs Questionnaire ²³ | Continuous | Baseline, 3 and 6 Months | Self-Report |
| • Self-Rated Health Status (Adapted from JHU) | Likert Items | Baseline, 3 and 6 Months | Self-Report |
| • Main Medical Problem, Concerns, and Goals | Open-Ended | Baseline, 6 Months | Self-Report |
| • Medication Adherence Measure (DOSE-Non-Adherence) ⁶⁸⁻⁷¹ | Continuous | Baseline, 3 and 6 Months | Self-Report |
| • ADL (Adapted from JHU) | Continuous | Baseline, 3 and 6 Months | Self-Report |
| • IADL (Adapted from JHU) | Continuous | Baseline, 3 and 6 Months | Self-Report |
| • PROMIS* – Isolation v2.0, Mobility v2.0, Pain Interference v1.1, Ability to Participate v2.0 ⁷² | Continuous | Baseline, 3 and 6 Months | Self-Report |

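### Does sharing a home visit with usual care leave the pilot's dose outcome undefined?

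*Combined protocol and SAP*

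**What the plan says.** Table 3 (Section 6.1) lists "Intervention Fidelity: Adherence, Dose, Quality" among the primary outcomes. The sources are audio recording, study documentation and self-report. Section 5.2 explains the dose element: "Exposure considers the number of intervention sessions and the time interventionists spent assisting participants".

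Section 5.1 states that "The study OT and RN will be the same clinicians who deliver CHHA CAU" and describes "each OT and RN visit lasting about 60-90 minutes". To fit both services in, "they will either lengthen the CAU visit or have a separate visit solely for the intervention". Section 2.2 adds that the intervention "can be delivered either at the end of a CAU RN and OT in-home session or at a separate in-home visit".

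Section 5.1 lets participants choose their dose, gives the number of visits as its example of dose, and sets the full dose at 6 OT and 5 RN visits. Section 5.4 tracks the proportion of participants who complete each portion and provides for routine audio recording. Section 9.4.1 analyses fidelity as yes/no completion of critical components. Section 9.1 promises univariate summaries of all outcomes in Table 3, and Section 9.5 rules out group comparisons and hypothesis tests.

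Differentiation is described in Section 5.2 as partly "a check to make sure that the participants in the intervention only received the plan intervention".

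**The concern.** Time is half of the Section 5.2 definition, yet no section provides a minutes field, a start and stop time, a marker for shared visits or a rule for dividing one. Section 5.1 also leaves open whether 60 to 90 minutes covers the intervention alone or the whole lengthened visit. Two analysts could therefore report different intervention times for the same visits.

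The ambiguity would fall unevenly. Early visits are the ones most likely to coincide with an open home health episode, so people who stop early could have a larger share of their time affected. People already discharged from the agency, whom Section 4.1 accepts, would have none affected. Because dose is chosen by the participant, its distribution is one of the things the pilot should report.

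Three smaller points sit alongside:
- Table 3 gives no arm for differentiation.
- Table 3 names neither the treating agency clinician nor the agency discharge date.
- Section 2.2 says every client will have agency nursing, while Section 4.1 admits people who do not.

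**Working it through.** The plan states no figure for intervention time, so there is none to reproduce. The check asks which parts of dose are open, how many visits could be shared, and what the minutes could amount to.

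**1. Which parts of dose are open**

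| Component | Source | Affected by a shared visit? |
|---|---|---|
| Number of sessions (6 + 5 = 11 at most) | Sections 5.1, 5.2 | No; a shared visit is one session |
| Proportion completing each portion | Section 5.4 | No |
| Completion of critical components | Section 9.4.1 | No |
| Interventionist minutes | Section 5.2 | Yes |

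**2. How many visits could be shared**

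Inputs: Table 1 for the first RN and OT visits, Table 2 for later spacing, and the agency's episode length in Section 5.1 (median 29 days, quartiles 17 and 47). Days from agency admission:

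- Shortest ideal spacing: RN 7, 14, 28, 42, 56; OT 14, 21, 28, 35, 49, 70.
- Longest ideal spacing: RN 14, 28, 56, 84, 112; OT 28, 42, 56, 70, 98, 126.

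| Episode ends on day | Visits inside it, longest to shortest spacing |
|---|---|
| 17 | 1 to 3 |
| 29 | 3 to 6 |
| 47 | 4 to 8 |

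The RN narrative in Section 5.1 puts the second RN visit 2 to 3 weeks after the first, whereas Table 2 says 1 to 2 weeks. On the narrative's spacing the day-29 count is 2 (RN 14; OT 28) to 5 (RN 7, 21; OT 14, 21, 28). The two intervals need to be reconciled in the text; this check does not choose between them.

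All these counts are ceilings. Clinicians may use separate visits. Section 2.2 expects many clients, not all, to receive agency OT. Randomization may come up to 28 days after discharge (Section 6.2.2), and the intervention starts only after it. The floor is 0.

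**3. What the minutes could amount to**

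Full-dose time T is 11 × 60 = 660 to 11 × 90 = 990 minutes. Let k be the number of shared visits and c the usual-care minutes in each. The documents give no value for c; assume 20 to 45. If 60 to 90 minutes is intervention time alone, overstatement = k × c / T:

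- k = 0: 0%
- k = 3, c = 20, T = 990: 60/990 = 6.1%
- k = 6, c = 45, T = 660: 270/660 = 40.9%
- With the RN narrative's spacing: 2 × 20/990 = 4.0% to 5 × 45/660 = 34.1%

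If 60 to 90 minutes already includes usual care, the denominator becomes T − k × c. The range over 3 to 6 shared visits is then 60/930 = 6.5% to 270/390 = 69.2%, again with a floor of 0%. The width of these ranges comes from the assumed c and the unknown k.

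**4. Differentiation**

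Section 5.2 ties it to intervention participants. The fidelity row in the Section 6.1 schedule is marked in the intervention column and blank in the comparator column. The footnote there says the intervention arm receives usual care as well, so concurrent usual care is expected and is not a departure. Doubt remains only at Days 90 and 180: those columns are headed for all participants, and Section 6.2.4 limits intervention feedback, but not study fidelity, to the intervention arm.

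**The case for a change.** The strongest case for a change is that minutes not noted at the visit may not be recoverable, and that noting them is cheap: a shared-visit marker with start and stop times at each session. Section 5.1 expects usual care to overlap with the intervention for most participants and wants the documentation to help assess study costs, so minutes may have a second use. The original CAPABLE excluded people receiving in-home therapy or nursing (Section 2.2), so its forms may not anticipate shared visits. For an early stopper whose visits were all shared, the same assumptions give 20/90 = 22% to 45/60 = 75% per visit.

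What stands is that the protocol states no division rule, and writing one down would be good practice. The rest has less force. Exposure is listed as a component of intervention fidelity, so counting the usual-care part of a visit as dose is not the natural reading. Section 2.2's ordering supplies a boundary. Random selection in Section 5.4 applies to scoring the recordings; recording itself is routine. The session forms are not among the documents, so it is unknown whether they already hold a time field.

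Treating clinician and agency discharge date would not settle how a visit's minutes are divided. The first matters mainly for contamination, and no between-group result is planned that contamination could distort. Adding them is a preference.

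**Conclusion.** No change to the plan is needed. This is missing operational detail in one component of one descriptive outcome, and it concerns only the planned 36 intervention participants. Session counts, completion proportions, adherence scoring and the clinical summaries are untouched.

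The size of any error in minutes cannot be set from the documents. It may be 0%. It reaches 41% only if 6 visits are shared, each carries 45 minutes of usual care, intervention time is 60 minutes per visit, and the whole visit is counted against the ordinary meaning of intervention exposure. The 69% figure further requires that the 60 minutes include usual care.

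A team preparing the dose summary would count the intervention part of each visit and say so. Differentiation's arm is clear except at the two follow-up visits, where the purpose given in Section 5.2 points to the intervention arm. The differing statements on agency nursing in Sections 2.2 and 4.1 are descriptive text to be reconciled editorially; no analysis depends on them. The conclusion rests on the study remaining a descriptive pilot. A later trial that related outcome to intervention minutes would need the convention stated in advance.
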